7.2.2 Serious Adverse Events

A serious adverse event (SAE) is any AE occurring at any dose that:

- Results in death;

CONFIDENTIAL

This document is confidential. Do not disclose or use except as authorized.

- Is life-threatening (i.e., in the opinion of the Investigator, the subject is at immediate risk of death from the AE);
- Requires inpatient hospitalization or prolongation of existing hospitalization (hospitalization is defined as an inpatient admission, regardless of length of stay);
- Results in persistent or significant disability/incapacity (a substantial disruption of the subject's ability to conduct normal life functions);
- Is a congenital anomaly/birth defect;
- Constitutes an important medical event

Important medical events are defined as those occurrences that may not be immediately life threatening or result in death, hospitalization, or disability, but may jeopardize the subject or require medical or surgical intervention to prevent one of the other outcomes listed above. Medical and scientific judgment should be exercised in deciding whether such an AE should be considered serious.

7.2.3 Attribution

The Investigator must determine the causal relationship between the administration of lenalidomide, the administration of MEC, and the occurrence of an AE/SAE as Not Related or Related as defined below:

Not Related: Means a causal relationship of the adverse event to IP administration is unlikely or remote, or other medications, therapeutic interventions, or underlying conditions provide a sufficient explanation for the observed event.

Related: Means there is a reasonable possibility that the administration of IP caused the adverse event. 'Reasonable possibility' means there is evidence to suggest a causal relationship between the IP and the adverse event.

Causality should be assessed as per the categories below and provided for every AE/SAE based on currently available information. Causality is to be reassessed and provided as additional information becomes available.

- Definite – The AE is *clearly related* to the study treatment.
- Probable – The AE is *likely related* to the study treatment.
- Possible – The AE *may be related* to the study treatment.
- Unlikely – The AE is *doubtfully related* to the study treatment.
- Unrelated – The AE is *clearly NOT related* to the study treatment.

If an event is assessed as possibly, probably or definitely related to a comparator, ancillary or additional IP that has not been manufactured or provided by Celgene, please provide the name of the manufacturer when reporting the event.

7.2.4 Duration, Action Taken and Outcome

For both AEs and SAEs, the Investigator will provide a record of the start and stop dates of the event

CONFIDENTIAL

This document is confidential. Do not disclose or use except as authorized.

The Investigator will report the action taken with IP as a result of an AE or SAE, as applicable (e.g., discontinuation, interruption, or dose reduction of IP, as appropriate) and report if concomitant and/or additional treatments were given for the event.

The Investigator will report the outcome of the event for both AEs and SAEs. All SAEs that have not resolved upon discontinuation of the subject's participation in the study must be followed until recovered (returned to baseline), recovered with sequelae, not recovered or death (due to the SAE).

7.3 Reporting Requirements for Specific Adverse Events

7.3.1 Abnormal Laboratory Values

An abnormal laboratory value is considered to be an AE if the abnormality:

- results in discontinuation from the study, and
- is judged to be of significant clinical importance

Regardless of severity grade, only laboratory abnormalities that fulfill a seriousness criterion need to be documented as a serious adverse event. If a laboratory abnormality is one component of a diagnosis or syndrome, then only the diagnosis or syndrome should be recorded on the AE page/screen of the CRF. If the abnormality was not a part of a diagnosis or syndrome, then the laboratory abnormality should be recorded as the AE. If possible, the laboratory abnormality should be recorded as a medical term and not simply as an abnormal laboratory result (e.g., record thrombocytopenia rather than decreased platelets).

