5.7 Criteria for Taking a Participant Off Study

Study subjects may withdraw their consent to participate in this trial at any time. Once withdrawn, the study subject will receive usual care considered standard and routine for their individual case.

Participants will be removed from study when any of the following criteria apply:

- Lost to follow-up
- Withdrawal of consent for data submission
- Death
- Completed all follow-up per protocol

The reason for taking a participant off study, and the date the participant was removed, must be documented in the case report form (CRF). The DF/HCC research team will update the relevant Off Treatment/Off Study information in OnCore. The Coordinating Center will update this information for external site participants.

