7. ADVERSE EVENTS: LIST AND REPORTING REQUIREMENTS

An adverse event (AE) is any noxious, unintended, or untoward medical occurrence that may appear or worsen in a subject during the course of a study. It may be a new intercurrent illness, a worsening concomitant illness, an injury, or any concomitant impairment of the subject's health, including laboratory test values, regardless of etiology. Any worsening (i.e., any clinically significant adverse change in the frequency or intensity of a pre-existing condition) should be considered an AE. A diagnosis or syndrome should be recorded on the AE page of the CRF rather than the individual signs or symptoms of the diagnosis or syndrome. An overdose, accidental or intentional, whether or not it is associated with an AE, or abuse, withdrawal, sensitivity or toxicity to an investigational product should be reported as an AE. If an overdose is associated with an AE, the overdose and adverse event should be reported as separate terms. All subjects will be monitored for AEs during the study. Assessments may include monitoring of any or all of the following parameters: the subject's clinical symptoms, laboratory, pathological, radiological or surgical findings, physical examination findings, or findings from other tests and/or procedures.

All AEs will be recorded by the Investigator from the first dose of study treatment until 28 days after the last dose of lenalidomide and those SAEs made known to the investigator at any time thereafter that are suspected of being related to lenalidomide. AEs and serious adverse events (SAEs) will be recorded on the AE page of the CRF and in the subject's source documents. All SAEs must be reported to Celgene Drug Safety within 24 hours of the Investigator's knowledge of the event by facsimile, or other appropriate method, using the SAE Report Form, or approved equivalent form.

Adverse event (AE) monitoring and reporting is a routine part of every clinical trial. The following list of reported and/or potential AEs (Section 7.1) and the characteristics of an observed AE (Section 7.2) will determine whether the event requires expedited reporting **in addition** to routine reporting.

CONFIDENTIAL

This document is confidential. Do not disclose or use except as authorized.

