Toxicity will be scored using CTCAE Version 4.03 for toxicity and adverse event reporting. A copy of the CTCAE Version 4.03 can be downloaded from the CTEP homepage (http://ctep.cancer.gov/protocolDevelopment/electronic_applications/ctc.htm#ctc_40). All appropriate treatment areas should have access to a copy of the CTCAE Version 4.03. All adverse clinical experiences, whether observed by the investigator or reported by the patient, must be recorded, with details about the duration and intensity of each episode, the action taken with respect to the test drug, and the patient's outcome. The investigator must evaluate each adverse experience for its relationship to MEC, relationship to lenalidomide, and for its seriousness. The investigator must appraise all abnormal laboratory results for their clinical significance. If any abnormal laboratory result is considered clinically significant, the investigator must provide details about the action taken with respect to the test drug and about the patient's outcome.

All adverse events experienced by participants will be collected from the time of the first dose of study treatment, through the study and until 28 days after the last dose of study treatment. Participants continuing to experience toxicity at the off study visit may be contacted for additional assessments until the toxicity has resolved or is deemed irreversible.

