7.4.4 Protocol-Specific Expedited Adverse Event Reporting Exclusions

For this protocol only, the AEs/grades listed below do not require expedited reporting to the Overall PI or the DFCI IRB. However, they still must be reported through the routine reporting mechanism (i.e. case report form).

- Hematologic toxicity of any grade does not need to be reported.
- Routine chemotherapy toxicity of any grade including nausea, diarrhea, constipation, vomiting, alopecia, mucositis, fatigue, grade 3-4 lab abnormalities that resolve to grade 0-2 with appropriate follow-up or intervention within 48 hours do not need to be reported.

Events not considered to be SAEs are hospitalizations for:

- A standard procedure for protocol therapy administration. However, hospitalization or prolonged hospitalization for a complication of therapy administration will be reported as an SAE.
- Routine treatment or monitoring of the studied indication not associated with any deterioration in condition

- The administration of blood or platelet transfusion as routine treatment of studied Indication. However, hospitalization or prolonged hospitalization for a complication of such transfusion remains a reportable SAE.
- A procedure for protocol/disease-related investigations (e.g., surgery, scans, endoscopy, sampling for laboratory tests, bone marrow sampling). However, hospitalization or prolonged hospitalization for a complication of such procedures remains a reportable SAE.
- Hospitalization or prolongation of hospitalization for technical, practical, or social reasons, in absence of an AE.
- A procedure that is planned (i.e., planned prior to starting of treatment on study); must be documented in the source document and the CRF. Hospitalization or prolonged hospitalization for a complication remains a reportable SAE.
- An elective treatment of or an elective procedure for a pre-existing condition unrelated to the studied indication.
- Emergency outpatient treatment or observation that does not result in admission, unless fulfilling other seriousness criteria above.

If an AE is considered serious, both the AE CRF and the SAE Report Form must be completed. For each SAE, the Investigator will provide information on severity, start and stop dates, relationship to study drugs, action taken regarding study drugs, and outcome.

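### Section 7.3.1 ties a laboratory adverse event to study discontinuation as well as clinical importance, which contradicts Sections 7 and 7.4.4 and risks under-recording

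*Combined protocol and SAP*

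**What the plan says.** Section 7.3.1 begins: "An abnormal laboratory value is considered to be an AE if the abnormality" meets two bulleted conditions. The first is that it "results in discontinuation from the study, and"; the second is that it "is judged to be of significant clinical importance". Further down, the same section says: "If the abnormality was not a part of a diagnosis or syndrome, then the laboratory abnormality should be recorded as the AE". It prefers a medical term, with thrombocytopenia as its example.

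Other current text bears on the same question:

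- **Section 7, AE definition.** An AE covers any impairment of the patient's health, "including laboratory test values, regardless of etiology". No discontinuation condition is attached.
- **Section 7, appraisal.** "The investigator must appraise all abnormal laboratory results for their clinical significance". For any result found clinically significant, the investigator must document the action taken on the drug and the outcome.
- **Section 7.4.4.** Hematologic toxicity of any grade, and grade 3-4 laboratory abnormalities that return to grade 0-2 within 48 hours, are exempt from expedited reporting. The section adds: "However, they still must be reported through the routine reporting mechanism (i.e. case report form").
- **Section 5.7.** "Participants will be removed from study when any of the following criteria apply". Four follow: loss to follow-up, withdrawal of consent for data submission, death, and completed follow-up.
- **Appendix B, Section 3.9.** All laboratory tests and hematological abnormalities count among the safety parameters.

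**The concern.** Section 7.3.1 is the section headed for laboratory values, so a data manager deciding whether a raised transaminase goes on the AE form will look there first. The test found there needs the patient to leave the study, which the protocol does not provide for on laboratory grounds. The other sections apply no such test, and nothing says which prevails.

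AE status governs what happens next: attribution to lenalidomide and to MEC (7.2.3), IRB reporting by grade (7.4.2), entry on the toxicity forms (7.5), and the unexpected grade 2 or higher AEs that may go to the data and safety monitoring committee (12.2). An abnormality that is not made an AE drops out of all of these. With several institutions entering data, two sites could treat the same laboratory result differently.

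**Working it through.** No stated figure depends on this rule, so the check is a comparison of the texts.

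**1. Connector.** The two bullets in 7.3.1 are joined by *and*. A value that is clinically important but does not lead to discontinuation meets one condition of two.

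**2. Can the first condition be met?** None of the four reasons in 5.7 is a laboratory result. In Table 4, removal from study appears only for rash (blistering at any grade, non-blistering at grade 4) and grade 4 neuropathy. Lenalidomide continues through grade 4 neutropenia and grade 3-4 thrombocytopenia. For acute kidney injury it is reduced or held. Under 5.6 and 10.4, patients who stop therapy early are still followed for up to 3 years.

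**3. A looser reading of the first condition.** Suppose that leaving the study means stopping protocol therapy under 5.5. The condition can then be met, but only by abnormalities that end treatment. One that is important yet managed by continuing, reducing, or holding and restarting the drug still fails. So does one that appears after the last planned dose on Day 10, when no protocol therapy is left to stop.

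**4. Three cases under each rule.**

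| Case | 7.3.1 read literally | Other sections |
|---|---|---|
| Isolated grade 3 transaminase rise, clinically significant, patient stays on study | First condition fails: not an AE | Within the Section 7 definition; details required |
| Grade 4 neutropenia, lenalidomide continued as in Table 4 | First condition fails: not an AE | On the CRF under 7.4.4 |
| Grade 3 electrolyte abnormality corrected within 48 hours | First condition fails: not an AE | On the CRF under 7.4.4 |

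The answers differ in every row.

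**5. Would *or* alone be enough?** It resolves the first row. It does not fully resolve the others, because 7.4.4 puts hematologic toxicity of any grade on the CRF with no test of importance. A low-grade cytopenia judged unimportant would still fall under two different rules.

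**6. What is not touched.** The primary endpoint (CR+CRp) rests on marrow and count criteria in 11.5, and the sample size rests on response rates. The hold rule in 13.1.1 counts delayed neutrophil or platelet recovery beyond day 45, which comes from the blood counts themselves. Its stated 7% is reproduced for 3 or more of 10 patients at a true rate of 10%:

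1 − (0.9^10 + 10 × 0.1 × 0.9^9 + 45 × 0.1^2 × 0.9^8) = 1 − (0.3487 + 0.3874 + 0.1937) = 0.0702.

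The other limb of that rule, unacceptable toxicities felt related to the regimen, has no such independent source.

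**The case against.** The strongest reply is that 7.3.1 says *if*, not *only if*, and that the rest of the protocol plainly wants laboratory toxicity recorded. Section 7, 7.4.4, 7.5 and Appendix B all point that way. So does the later sentence in 7.3.1 on stand-alone abnormalities, whose own example, thrombocytopenia, does not stop lenalidomide under Table 4. A reader might infer from the two bullets that almost no laboratory toxicity can be recorded. The documents do not support that, because these other provisions require or allow recording without any discontinuation.

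Three further points have weight. The protocol uses the word *study* loosely: Table 4 removes patients from study for reasons that 5.7 does not list. Much organ toxicity would be entered as a diagnosis, such as acute kidney injury, rather than as a laboratory value. Weekly blood counts and chemistry are required data under Table 6, so the raw values exist.

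The contradiction remains. If the bullets set no limit they do no work, and a site will naturally read them as the threshold. The sentence on stand-alone abnormalities can be read as choosing the term once that threshold is met; if it overrides the bullets instead, 7.3.1 contradicts itself. Raw values are not graded, attributed AEs. The looser sense of *study* narrows the problem without removing it, as step 3 shows.

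**Conclusion.** The point holds as an internal contradiction with a real risk of under-recording. Taken literally, 7.3.1 excludes isolated laboratory abnormalities that Sections 7 and 7.4.4 would have recorded. Those most exposed are hepatic, renal and electrolyte abnormalities that are clinically important but neither end participation nor form part of a recorded diagnosis.

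The size cannot be stated, because it depends on how many sites follow 7.3.1 over the other sections, and the documents do not say. A reader might try to size it by the share of the AE collection period that falls after the last dose. That does not work: it concerns stopping treatment rather than leaving the study, and a share of days is not a share of events lost.

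The conclusion assumes that at least some sites treat 7.3.1 as the operative rule for laboratory values. It bears on the completeness and between-site consistency of the safety data. Efficacy conclusions, the sample size and the count-recovery part of the hold rule stand as they are. The change should be made, since the defect is in a stated rule and the correction is small.

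**What to change.** In 7.3.1, change *and* to *or*, so that an abnormal laboratory value is an AE if it leads to discontinuation or is judged clinically important. Add one sentence saying that the events listed in 7.4.4 are entered on the CRF whether or not either condition is met. A short cross-reference from the AE definition in Section 7 to 7.3.1 would confirm that the sections state one rule.

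The cost is one word, one sentence and a cross-reference, plus slightly more AE recording at the sites. No assessment is added, because the counts and chemistry are already scheduled and the investigator must already appraise abnormal results.

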7.3.2 Second Primary Malignancies

Second primary malignancies will be monitored as events of interest and must be reported as serious adverse events the subject is in. This includes any second primary malignancy, regardless of causal relationship to study drugs occurring at any time for the duration of the study, from the time of signing the ICD for at least 3 years from the date the last subject is enrolled into the study. Events of second primary malignancy are to be reported using the SAE report form and must be considered an "Important Medical Event" if no other serious criteria apply; these events must also be documented in the appropriate page(s) of the CRF (i.e., AE and SPM CRF) and subject's source documents. Documentation on the diagnosis of the second primary malignancy must be provided at the time of reporting as a serious adverse event (e.g., any confirmatory histology or cytology results, X-rays, CT scans, etc.).

7.3.3 Pregnancies

Pregnancies and suspected pregnancies (including a positive pregnancy test regardless of age or disease state) of a female subject occurring while the subject is on study treatment, or within 28 days from last study treatment, are considered immediately reportable events. Study treatment is to be discontinued immediately. The pregnancy, suspected pregnancy, or positive pregnancy test must be reported to the Coordinating Center for submission to Celgene Drug Safety

CONFIDENTIAL

This document is confidential. Do not disclose or use except as authorized.

immediately by facsimile, or other appropriate method, using the Pregnancy Initial Report Form, or approved equivalent form. The female subject may be referred to an obstetrician-gynecologist (not necessarily one with reproductive toxicity experience) or another appropriate healthcare professional for further evaluation.

The Investigator will follow the female subject until completion of the pregnancy, and the Coordinating Center and Celgene notified immediately about the outcome of the pregnancy (either normal or abnormal outcome) using the Pregnancy Follow-up Report Form, or approved equivalent form.

If the outcome of the pregnancy was abnormal (e.g., spontaneous or therapeutic abortion), the Investigator should report the abnormal outcome as an AE. If the abnormal outcome meets any of the serious criteria, it must be reported as an SAE to Celgene immediately by facsimile, or other appropriate method, within 24 hours of the Investigator's knowledge of the event using the SAE Report Form, or approved equivalent form.

All neonatal deaths that occur within 28 days of birth should be reported, without regard to causality, as SAEs. In addition, any infant death after 28 days that the Investigator suspects is related to the in utero exposure to the IP should also be reported to Celgene Drug Safety immediately by facsimile, or other appropriate method, within 24 hours of the Investigator's knowledge of the event using the SAE Report Form, or approved equivalent form.

If a female partner of a male subject taking investigational product becomes pregnant, the male subject taking lenalidomide should notify the Investigator, and the pregnant female partner should be advised to call their healthcare provider immediately.

7.3.4 Overdose

Overdose, as defined for this protocol, refers to chemotherapy drug dosing only.

On a per dose basis, an overdose is defined as the following amount over the protocol-specified dose of lenalidomide, mitoxantrone, etoposide, or cytarabine assigned to a given patient, regardless of any associated adverse event or sequelae:

- PO-any amount over the protocol-specified dose
- IV-10% over the protocol-specified dose

On a schedule or frequency basis, an overdose is defined as anything more frequent than the protocol required schedule or frequency.

On an infusion rate basis, an overdose is defined as any rate faster than the protocol-specified rate. Complete data about drug administration including any overdose, regardless of whether the overdose was accidental or intentional, should be reported in the case report forms.

The Coordinating Center will submit reports of all suspected or confirmed pregnancies, pregnancy outcomes, neonatal deaths or overdoses to Celgene Drug Safety immediately by

facsimile, or other appropriate methods on behalf of the participating site.

Coordinating Center
[REDACTED]

Celgene Drug Safety Contact Information:

Celgene Corporation
Global Drug Safety and Risk Management
[REDACTED]

